| | Index imaging (before procedure) | Index Imaging (After procedure) |
|--------------------------------------|---|--|
| USG/CT/MRI: | | |
| Date/ PGI No. | | |
| Collections: PN/EPN/PN+EPN | | |
| Location of collection: | | |
| Size of collection: | | |
| Extension: | | |
| Gas configuration within collection: | | |
| Vascular complications: | | |
| Pleural effusion/ ascites: | | |
| CTSI/ modified CTSI | | |
| Clinical success (Y/N) | | |

Follow up Imaging:

| | | | | |
|--------|---|---|---|---|
| | 1 | 2 | 3 | 4 |
| CT/MRI | | | | |

| | | | | |
|-------------------------------------|--|--|--|--|
| Date/ PGI No. | | | | |
| Collections: PN/EPN/PN+EPN | | | | |
| Location of collection: | | | | |
| Size of collection: | | | | |
| Extension: | | | | |
| Gas configuration within collection | | | | |
| Vascular complications: | | | | |
| Pleural effusion/ascites: | | | | |
| Clinical success (Y/N) | | | | |

Indication of Drainage:

1. Positive gram stain/culture
2. Gas configuration within collection
3. Clinically suspected infection
4. Compressive symptoms (gastric outlet obstruction or biliary obstruction)
5. Pressure symptoms (early satiety, weight loss)
6. Persistent pain abdomen

Disease characteristics at time of drainage:

Days from onset of acute pancreatitis:

Days from hospitalization:

Ongoing Fever: (Y/N); Days:

Ongoing SIRS: 1/2/3/4: Days:

Ongoing OF: (Y/N); Type of organ failure (ALI/AKI/CVSF); Days of ongoing OF:

Index drainage by EUS:

| | |
|----------------------------------|--|
| Date | |
| Size of collection | |
| Percentage of necrosis | |
| Stent used | |
| Any Periprocedural complications | |

Randomization:

A. Oral feed:

Nutritional assessment:

| Date | Day 0 | Day 1 | Day 2 | Day 5 | Day 8 | Day 11 | Day 14 |
|-----------------|-------|-------|-------|-------|-------|--------|--------|
| Calorie intake | | | | | | | |
| Protein intake | | | | | | | |
| Change in route | | | | | | | |

| Weight | Day 0 | Day 14 |
|--------|-------|--------|
| | | |

| Date | Day 0 | Day 7 | Day 14 |
|---------------------------------|-------|-------|--------|
| Albumin | | | |
| CRP | | | |
| Total length of hospitalization | | | |

| Date | Adverse events related to feed |
|------|--------------------------------|
| | |
| | |
| | |
| | |
| | |
| | |
| | |

| Date | Indication | NCD used | Stent migration/ Blockage | Stent removal/ PS placement | Complete necrosectomy | Complication |
|-------|------------|----------|------------------------------|--------------------------------|-----------------------|--------------|
| DEN 1 | | | | | | |
| DEN 2 | | | | | | |
| DEN 3 | | | | | | |

B. Metal Stent NJ feed:

Nutritional assessment:

| Date | Day 0 | Day 1 | Day 2 | Day 5 | Day 8 | Day 11 | Day 14 |
|-----------------|-------|-------|-------|-------|-------|--------|--------|
| Calorie intake | | | | | | | |
| Protein intake | | | | | | | |
| Change in route | | | | | | | |

| Weight | Day 0 | Day 14 |
|--------|-------|--------|
| | | |

| Date | Day 0 | Day 7 | Day 14 |
|---------------------------------|-------|-------|--------|
| Albumin | | | |
| CRP | | | |
| Total length of hospitalization | | | |

| Date | Adverse events related to feed |
|------|--------------------------------|
| | |
| | |
| | |
| | |
| | |
| | |
| | |

| Date | Indication | Stent migration/ Blockage | Stent removal/ PS placement | Complete necrosectomy | Complication |
|-------|------------|------------------------------|--------------------------------|-----------------------|--------------|
| DEN 1 | | | | | |
| DEN 2 | | | | | |
| DEN 3 | | | | | |

Parameters after Index Procedure:

| | | Day 0 | Day 3 | Day 7 | Day 14 | Day 21 | Day 28 |
|----------------|------|-------|-------|-------|--------|--------|--------|
| Fever | | | | | | | |
| SIRS | | | | | | | |
| OF | ALI | | | | | | |
| | AKI | | | | | | |
| | CVSF | | | | | | |
| Hemoglobin | | | | | | | |
| TLC | | | | | | | |
| CRP | | | | | | | |
| APACHE II | | | | | | | |
| BISAP | | | | | | | |
| Urea/Crt | | | | | | | |
| T. Bil/ D. Bil | | | | | | | |
| Albumin | | | | | | | |
| AST/ALT/ALP | | | | | | | |
| Procalcitonin | | | | | | | |
| Blood Culture | | | | | | | |
| NCD culture | | | | | | | |
| PCD culture | | | | | | | |

Fluid Analysis:

| | Total cells/ Differential cells | Glucose | Protein/ Albumin | Amylase/ Lipase | LDH | CA 19.9 | Culture |
|-----------------------|---------------------------------------|---------|---------------------|--------------------|-----|---------|---------|
| Ascitic fluid | | | | | | | |
| NCD / WON fluid | | | | | | | |
| PCD fluid | | | | | | | |

Antibiotics:

| No | Antibiotics/ Antifungal | Culture based (Y/N) | Duration | No | Antibiotics/ Antifungal | Culture based (Y/N) | Duration |
|----|----------------------------|---------------------------|----------|----|----------------------------|------------------------|----------|
| 1 | | | 4 | | | | |
| 2 | | | 5 | | | | |
| 3 | | | 6 | | | | |

Requirement of Percutaneous drainage catheter: (Y/N)

Indication: Site: Size:

Duration:

Requirement of surgical intervention: (Y/N)

Indication: Site: Size:

Duration:

Complications during any intervention:

Technical success: (Y/N)

Clinical success: (Y/N)

Time duration at clinical success: (Y/N)

Metal stent exchanged with plastic stent: (Y/N)

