Three randomized controlled trials comparing nasojejunal and nasogastric feeding routes in patients with severe acute pancreatitis found no significant differences in terms of feeding tolerance, complication rates, or mortality [38-40]. Four meta-analyses [41-44] have concluded that nasogastric tube feeding is a feasible, safe, and well-tolerated approach in patients with severe acute pancreatitis. Compared to nasojejunal feeding, it does not lead to higher rates of complications, mortality, recurrence of refeeding pain, or extended hospital stay. Unfortunately, to date, there have been no published studies specifically addressing the topic of nutritional support in patients with pancreatic collections treated using minimally invasive approaches. In a large Dutch trial demonstrating the superiority of the endoscopic approach over the surgical step-up strategy [84], specific data on nutritional support were not reported. However, all patients were provided with oral nutrition when tolerated. In cases of oral intolerance, enteral nutrition was delivered via a nasojejunal feeding tube, and parenteral nutrition was administered when enteral nutrition was contraindicated [45].

Aims and Objectives:

Aim:

To compare outcomes of Nasojejunal feeding vs oral feeding following endoscopic transluminal drainage in patients with symptomatic walled-off necrosis

Primary Objectives:

1. To compare the rate of nutritional failure at Day 14 between Nasojejunal and oral feeding post endoscopic transmural drainage of WON.

Secondary Objectives:

1. To compare infection rates, need for antibiotic escalation and new onset organ failure
2. To compare re-intervention needs and hospital stay duration
3. To compare patient weight, serum albumin and inflammatory markers (CRP)
4. To compare GI complications (Vomiting, diarrhoea, aspiration pneumonia, feeding intolerance)
5. To compare patient reported outcomes (appetite, pain ,quality of life)

Materials and Methods:

Study design

The study will be a prospective, open label, single centre, randomized controlled trial. It will be conducted in the Department of Gastroenterology, PGIMER, from July 2025 to December 2026

Study Population:

All patients presented to PGIMER with WON due to acute pancreatitis requiring EUS guided transluminal drainage will be screened for inclusion criteria.

Inclusion criteria

1. Patients of acute pancreatitis (AP) with 18-75 years of age

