Randomization: Patients needing EUS guided drainage with LAMS for symptomatic WON will be randomized once they fulfil inclusion criteria. Computer generated randomization assignments will be provided in advance using block randomisation and placed in sequentially numbered sealed envelopes. They will be opened during the procedure to determine treatment allocation.

Study flow:

Patients of AP with infected WON who are planned for EUS guided transluminal drainage by LAMS will be screened for inclusion criteria. Patients who fulfilled inclusion criteria will be randomized into either Nasojejunal (NJ) feeding or oral feeding after informed consent.

[figure not shown]
Sample size:

Since it is a pilot study and in a year the unit treats approximately 80-100 patients with WON and therefore considering exclusions a feasibility sample size of 20 in each arm will be taken.

Techniques:

Initial diagnostic EUS:

EUS examination will be done under conscious sedation using intravenous midazolam. Linear scanning echoendoscope (EG-3870 UTK linear echoendoscope, Pentax Inc., Tokyo, Japan or

UCT180 linear echoendoscope, Olympus Optical Co Ltd, Tokyo, Japan) will be used at a frequency of 7.5 MHz. The WON and surrounding areas will be first carefully scanned on EUS with special emphasis on size as well as detailed morphology of WON. Colour Doppler will be used to detect any intervening vascular collaterals.

Quantification of solid necrotic debris on EUS:

The echogenic material present in the WON is suggestive of solid necrotic debris. An attempt to quantify the amount of solid debris as percentage of total size of collection will be done. The quantification of the solid debris will be an approximate visual judgment of the endoscopist.

Randomization:**A. Nasojejunal (NJ) feeding group:**

- Patients randomized to this group will have NJ placement within 24 hours post-drainage.
- NJ will be placed endoscopically
- NJ position will be confirmed by Abdominal X-ray (AXR)
- Standard formula feed will be initiated immediately after placing and confirming the NJ position with a rate of
 - First 24 hours : 25 ml/hr
 - Between 24-48 hours : 50 ml/hr
 - Between 48-72 hours: increase to full nutrition
 - After 72 hours: Full nutrition
- Full nutrition is defined as an energy target of 30kcal/kg/day

.

B. Oral feeding group:

- Patients randomized to this group will initiated on oral feed post procedure as tolerated.

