- Patient will be started on oral liquid then on soft diet. Escalation will be guided based on feed tolerance. Oral diet will be supplemented with parenteral nutrition if caloric intake is <60% of target calorie at Day 5.

Nutritional failure at Day 14:

Definition:

- <75% calorie requirements are met
- Need for parenteral nutrition
- Severe GI intolerance requiring feed modification

Infectious complications:

The patient should have signs of bacterial infections/fungal infections i.e. body temperature $>100^0$ F and raised leukocytes, CRP, Procalcitonin, beta-D glucan and galactomannan.

| Infection | Definition |
|-------------------------------------|---|
| Infected pancreatic necrosis | Positive culture after first percutaneous drainage procedure of collection with (peri-) pancreatic necrosis |
| Bacteremia | Positive blood culture Positive culture in 1 blood culture. In case of coagulase negative staphylococci or other non-virulent micro-organisms at least 2 blood culture bottles are mandatory. |
| Pneumonia | Coughing, dyspnoea, radiography with infiltrative abnormalities and positive culture in sputum. On the intensive care unit, a positive endotracheal culture is mandatory |
| Sepsis | SIRS and positive blood culture |
| | |

Statistical analysis:

All patients after randomization will be evaluated for primary and secondary endpoints. Data will be explored for any outliers, errors and missing values. When data will be normally distributed, continuous variables will be compared using Student's t-test. For skewed data, Mann-whitney test will be used. Quantitative data will be described as median with range and mean with standard deviation. Categorical data will be shown as proportions. Multiple linear regression analysis will be performed to identify risk factors for requirement of additional intervention after initial drainage procedure. 95% confidence interval will be taken as a cut-off for significance. Intention to treat and per-protocol analysis will be performed. The analysis was performed using Statistical Packages for the Social Sciences (SPSS Inc, Chicago, IL, version 22.0 for windows).

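### The only form field that fits the GI events of secondary objective 4 is limited to feed-related events, with no attribution rule, and no field is dedicated to NJ-tube events

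*Protocol*

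**What the plan says.** **Objective.** Secondary Objectives, item 4, reads "To compare GI complications (Vomiting, diarrhoea, aspiration pneumonia, feeding intolerance", where the list ends. It sets no condition that an event be caused by the feed.

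**Form.** In the Thesis Proforma, each arm has a blank table of dates and events headed "Adverse events related to feed". The two tables are identical. Neither lists events, grades them or says how relatedness is to be judged.

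**Design.** The trial is described under Study design as a "prospective, open label, single centre, randomized controlled trial". No blinded assessor is named, and the protocol does not say who completes the form.

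**Other harm fields.** The form also has "Any Periprocedural complications" for the index drainage, a complication column for each necrosectomy session, fever, SIRS, organ failure and cultures on set days to Day 28, "Change in route" on seven days from Day 0 to Day 14, and "Complications during any intervention". None of these depends on a link to the feed.

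**NJ tube.** The NJ arm's instructions state that "NJ will be placed endoscopically". No field on the form names tube dislodgement, blockage, replacement or nasal injury.

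**The concern.** The objective asks how often these events occur in each arm. The form asks only for those that someone has linked to the feed. The two differ whenever an event has another plausible cause, and the protocol says that it often may: its literature section on the limits of oral feeding attributes vomiting, pain and bloating to pressure from the collection. Every participant has such a collection and has just had it drained. Whether a given episode of vomiting belongs in the table is therefore a matter of judgement, and in an open-label trial that judgement can be made with the arm known.

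Two things are at stake. Events judged unrelated are never written down, so no later analysis can recover them. And if the judgement runs differently in the two arms, a difference can appear where none exists, or a real one can be hidden. Separately, problems with the feeding tube are a burden that only the NJ strategy carries, and the form has no reliable place to count them.

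**Working it through.** The protocol gives no figure on this point, so there is none to reproduce. The check has three parts.

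**1. Which fields can hold the objective 4 events?**

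| Event | Table limited to feed-related events | Any other field |
|---|---|---|
| Vomiting | Yes, if attributed to feed | None |
| Diarrhoea | Yes, if attributed to feed | None |
| Aspiration pneumonia | Yes, if attributed to feed | Indirect only (fever, SIRS, organ failure) |
| Feeding intolerance | Yes | Indirect only (calorie intake, route change) |

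The infectious complications table does define pneumonia without regard to cause, as "Coughing, dyspnoea, radiography with infiltrative abnormalities and positive culture in sputum". But the follow-up table to Day 28 has no row for pneumonia, chest radiography or sputum culture.

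**2. Which fields can hold NJ-tube events?**

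- A complication of endoscopic placement fits "Complications during any intervention".
- A lost tube that leads to oral or parenteral feeding would show under "Change in route".
- A tube that blocks or dislodges on the ward and is replaced by another NJ tube leaves the route unchanged. It is not clearly a complication during an intervention, and as a device event it falls outside the wording of the feed heading.

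By contrast, the form does have a column for stent migration or blockage at each necrosectomy session.

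**3. How large could the effect be?** All rates here are assumptions; only the 20 per arm comes from the protocol (Sample size).

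Recorded rate = true rate × share attributed to feed.
False difference = true rate × (share in one arm − share in the other), when the true rates are equal.

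With shares of 90% and 60%:

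- True rate 30%: 0.30 × 0.90 = 27%, 0.30 × 0.60 = 18%, difference 9 points.
- True rate 50%: 0.50 × 0.90 = 45%, 0.50 × 0.60 = 30%, difference 15 points.
- True rate 70%: 0.70 × 0.90 = 63%, 0.70 × 0.60 = 42%, difference 21 points.

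The last three columns give the probability of a significant two-sided Fisher exact test at 0.05 with 20 per arm, by full binomial enumeration. Fisher's test is chosen for illustration.

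| True rate, both arms | All events recorded | 90% v 60% attributed | 90% v 40% attributed |
|---|---|---|---|
| 30% | 2.5% | 5.6% (9 points) | 13.5% (15 points) |
| 50% | 2.0% | 10.1% (15 points) | 29.3% (25 points) |
| 70% | 2.5% | 16.0% (21 points) | 47.5% (35 points) |

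With equal attribution (90% in both arms, or 60% in both), the false difference is 0 and the rejection probability stays at 2.2% to 2.5%. Events are still under-counted: at 60% attribution, a true 50% is recorded as 30%.

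**The case against.** The best defence is that the heading is a label, not a filter. The table sits within the nutritional assessment, is the same in both arms, and may simply be where the tolerance events of objective 4 are meant to go. The protocol describes no causality step, and its statistical section says that all randomised patients will be evaluated for the secondary endpoints. Feeding intolerance is feed-related by its nature, so the heading hardly restricts that item. Tube events are not part of objective 4. And this is one of several secondary objectives in a pilot of 20 per arm.

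Some of this stands. The documents show a heading that restricts, not an established practice of restricting, and adding tube rows extends the harms recorded; it does not repair a stated outcome. But staff fill in a form by its headings, and nothing elsewhere tells them to enter vomiting or diarrhoea that they ascribe to the collection or the procedure.

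A reader might go further in four ways that the documents do not support:

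- *Only feed-related adverse events are recorded in this trial.* Not so. Procedural and intervention complications, fever, SIRS, organ failure and cultures are recorded without any such link.
- *NJ-tube harms have no place on the form.* Too strong. Some would appear under intervention complications or route change, and staff might enter others in the free text. What is missing is a dedicated field.
- *The comparison is biased because unblinded staff judge relatedness.* The open-label design allows this, but the protocol does not say who completes the form, and nothing shows that attribution would differ by arm or in which direction.
- *The primary endpoint is compromised, because severe GI intolerance is one of its components.* The protocol does not say that this component is taken from this table, and calorie intake and route change are recorded separately.

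**Conclusion.** The point holds in limited form. Objective 4 and the form do not match: the objective has no relatedness condition, while the only field that fits its events has one, without a rule for applying it. If the heading is followed, the consequence is under-counting. Bias between arms follows only if attribution differs by arm.

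The false differences of 9 to 21 points (90% v 60% attributed) and 15 to 35 points (90% v 40%) rest wholly on assumed event rates and attribution shares. They show what the form would allow, not what will happen. For the NJ tube, the gap is the lack of a dedicated field, which matters most for a tube that fails on the ward and is replaced like for like.

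The statistical analysis plan is not at hand, but it could not close this gap, since it cannot restore events that were never recorded. The change is worth making, though it concerns a secondary objective and alters neither the sample size nor the analysis of the primary endpoint.

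**What to change.** Revise the form in both arms:

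1. Replace the restricted free-text table with a dated checklist of vomiting, diarrhoea, aspiration pneumonia and feeding intolerance, completed whatever the suspected cause. Use the protocol's existing pneumonia criteria as part of the entry for aspiration pneumonia.
2. Put the judgement of relatedness in a separate column.
3. State that the comparison for objective 4 uses all recorded events, regardless of relatedness.
4. Add rows for NJ-tube events (dislodged, blocked, replaced, nasal injury) and report them descriptively as harms of the NJ strategy.

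The cost is a revised form and a little more daily recording. Treatment and sample size do not change. The revision works best before enrolment, because events already missed cannot be reliably recovered.
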